## **5.6 Premature Termination or Suspension of Study**

This study may be suspended or prematurely terminated if there is sufficient reasonable cause. Written notification, documenting the reason for study suspension or termination, will be provided by the suspending or terminating party to the PI or NIDCR. If the study is prematurely terminated or suspended, the principal investigator will promptly inform the IRB and will provide the reason(s) for the termination or suspension. The study will also inform participating clinics. Since this is a self-management behavioral study with minimal risks, there are few possible reasons for termination or suspension of the study.

This study will be stopped prior to its completion if:

- The intervention is associated with adverse effects that call into question the safety of the intervention;
- Difficulty in study recruitment or retention will significantly impact the ability to evaluate the study endpoints;

- Any new information becomes available during the trial that necessitates stopping the trial; or
- Other situations occur that might warrant stopping the trial.

## 5.7 Study Behavioral or Social Intervention(s) Description

### 5.7.1 PACT Program

The Personalized Activated Care and Training (PACT) program is a self-management program designed to help participants with TMD pain understand the “big picture” of their condition, how to reduce risk factors and enhance protective factors using a cognitive-behavioral training approach. Eight lessons are delivered over 8-weeks. The program is designed to improve participant engagement, understanding, and compliance. Activities in each module will include improving understanding of TMD, its causes and the role of self-care in healing. Activities are designed to teach concepts on how to reduce risk factors, improve protective factors, encourage healing, restore range of motion, reduce pain, and improve the healthy use of the jaw in everyday life. Risk factors include: behavioral factors (e.g., repetitive strain, muscle tension, postural habits, chemical use, diet), emotional factors (e.g., anxiety, depression), cognitive factors (e.g., poor understanding, poor coping strategies, catastrophizing), social factors (e.g., stress, conflict, abuse), and environmental factors (e.g. environmental risk and injury) that can lead to delayed recovery. Protective factors include: exercise, relaxation, coping, self-efficacy, participant beliefs (e.g., perceived control over pain), and social support that can lead to more positive outcomes. **APPENDIX B: CONTENT AND TEXT FOR INTRODUCTORY VIDEO** provides more detailed information about each lesson.

Questionnaires to assess risk factors briefly in each realm for each patient in the PACT program will also be administered online. Training patients on risk and protective factors are integrated to provide more personalized self-management training plan for the participant and supported by the coach.

The PACT program will be compared to a usual self-care focused on traditional strategies implemented with a written handout at the initial visit to encourage healing and recovery. This information will be used as the content for usual self-care in the study. The format of usual self-care materials will match the format of the PACT program. Both the PACT program and the written handout will available through the web-based platform to encourage participant retention and to track the access of usual self-care training materials.

### 5.7.2 Control Group

The control group will be able to download usual self-care pdfs from the website. Usual self-care strategy in pdf form will include rest, heat/ cold, soft diet, palatal tongue posture, reduce gum chewing, and avoid strain during opening the jaw. A summary of self-care materials for TMD that is used in the HPDG clinics is presented in **APPENDIX C: TRADITIONAL SELF-CARE PROTOCOL**.

## 5.8 Administration of Intervention

Course material will be administered through an on-line website program. The focus will be on both didactic knowledge and interactive content. The use of a health coach is also integrated into the online intervention and will be conducted through telephone calls with study participants on a regular basis determined by the coach and participant at the start of

the intervention period (see Appendix D for Health Coach Phone Protocol).

*Health Coach.* The self-management program will also be supported by 3 three health coaches who have specialized training in health coaching with additional training in TMD and chronic pain. Health coaches are already employed within HealthPartners to engage patients with several chronic illnesses. Three of these trained coaches will provide the coaching services for the study. An agreement or pact with the participant is implemented by the health coach to ensure understanding of self-management program and the importance of each step. An initial phone call is held with the participant to ensure that they understand the basics on the self-management training program and how to use the information technology. Phone support is provided on a weekly basis to answer questions and encourage understanding and adherence to the self-management program. A minimum phone contact of 3 calls including the initial call, touch base call, and final call is required. If a participant is very engaged in the health coaching, a maximum phone contact will be two times per week for three months. The average length of calls is intended to be initial call of 30-60 min. as needed with follow-up calls of 30 min. Audio recordings of the telehealth visits will not be completed since the analysis of the coaching model itself is not the focus of study outcomes and it may interfere with coaching. Fidelity of the health coaching component of the PACT program will be assessed by review of the coaching logs, including the number of contacts and adherence to the coaching model with discussion of goals, barriers, understanding, and motivation. Discussions will be held with health coaches to assess their experience and how they perceive it contributes to the overall the PACT program.

## **5.9 Procedures for Training Interventionists and Monitoring Intervention Fidelity**

The study intervention is a self-administered online self-management program supported by a health coach, in this context the interventionists for the PACT program are health coaches.

*Training.* The study coordinator and health coaches will receive training on the study protocol, PACT manual, and the care of temporomandibular disorders including self-management. This includes participating in IRB training, study protocol training, as well as an on-line MOOC course on preventing chronic pain ([www.coursera.org/learn/chronic\\_pain](http://www.coursera.org/learn/chronic_pain)). Study staff are required to pass examinations after completing this online course in order to serve as health coaches for this study. Study staff will also participate in the on-line PACT training program themselves as if they were participants. Then, 3 one hour or more discussion groups and training sessions with the health coaches will occur before, during and after the study. The health coaches will be supervised by the Principal Investigator, [name], and [name] as well as our consultant [name], Director of the Health Coaching training program at the University of Minnesota. These investigators will meet with health coaches each month to review their discussions with patients, their barriers, and implementation of the program. Their notes about the health coaching experiences will be discussed also.

In this study, Health Coaching is considered a relationship-centered, client-driven process designed to facilitate and empower a client to achieve self-determined goals related to health and overall well-being. While the participant's primary goal in this study is to improve their TMD pain and function, the coaching model includes the selection of goals and exploration on how to achieve them based on the participants' preferences. Individuals may be just beginning to consider life change, may be exploring aspects of preparing for a change, or may be ready to implement actual actions. In a safe and consistent space, participants can explore their thoughts, emotions, and actions, in a way that allows them to recognize the power of their own

choices to impact their pain and well-being. Health Coaching is a methodology that is different from but supported by the on-line health education in the PACT program and the counseling or therapy received by health professionals such as the dental provider and physical therapist. It is designed to work well in combination with those care strategies. By applying clearly defined knowledge and skills, they support individuals or groups in mobilizing their internal strengths and external resources to achieve sustainable changes in beliefs or behaviors. Health Coaching has the potential to help individuals, families, and groups achieve improved health and wellbeing.

*Fidelity of Health Coaching.* Fidelity to the coaching model will be assessed by analysis of the interviews and review of the coaching documentation with a focus on: 1) development a positive supportive health coaching relationship, 2) clarification of goals, 3) identifying strengths/resources/barriers, 4) monitoring completion of weekly modules, 5) inquiring about usefulness of information.

*Monitoring Protocols and Interventions.* Once the participant has enrolled in the TMD Pain Study and been randomized to the PACT program or the control arm, the study coordinator will monitor compliance and adherence to the study protocol. The study coordinator will do this by monitoring completion of the baseline and follow-up questionnaires answer questions and the SRC will send reminders to participants, as needed. Compliance and adherence will be assessed by the number of on-line sessions that the study participants in both arms participate, data that will be collected each week by monitoring on-line access and health coaching reports.

## **5.10 Assessment of Subject Compliance with Study Intervention**

The assessment of subject compliance with study intervention corresponds to one of our feasibility aims (see section 3.2.b) Compliance and adherence to the study intervention will be assessed by the number of on-line sessions (or self-care materials accessed online by control arm) that the study participants in both arms participate in and self-reported program activities (PACT arm only), Information about the on-line sessions will be collected each week by monitoring on-line access.

## **5.11 Concomitant Medications/Treatments**

The study will allow the concomitant use of other TMD treatments such as medication, splints, and physical therapy. The use of these treatments will be monitored during study implementation. This will allow us to determine the likely extent of concomitant use of medication, splints, and physical therapy during the PACT program and, in the larger study, account for their effects in final analyses.

## 6 STUDY SCHEDULE

The Schedule of Events table, found in APPENDIX A, provides an overview of initial, intermediate, and final study visits (including all contacts with participants; e.g., telephone, website, screening, and other contacts) Two weeks is the acceptable time windows for each of the activities. If each phase is not completed within this 2 week window after consenting, the project manager will call the patient to remind them and determine if there are barriers to completion.

### 6.1 Screening (Week -1 Pre-Intervention)

After obtaining verbal consent, the TMD screener form (APPENDIX E) will be administered specific points of medical history, eligibility criteria, and contact information will be recorded. Screening will occur by telephone and the contact will be documented on the screening form. Inclusion and exclusion criteria will be reviewed and documented including the TMD screener form and exclusions such as serious co-morbid conditions or medical history that contributing to pain or prevent participation e.g. pregnancy, psychiatric disorder, or systemic pain disorder.

All potential participants will be given a verbal explanation of the study, and will be screened by phone to ensure eligibility. If they meet eligibility criteria, a packet of study materials (including an overview of the study, consent, and HIPAA privacy information) will be emailed to the potential participant, and their contact information will be added to the coordinator contact list.

### 6.2 Enrollment/Baseline Visit (Website Visit 1, Week 0)

1. The SRC will contact the participant to review the consent form, HIPAA privacy information, study information, and the risk and benefits for participation including the cost and compensation and will confirm understanding of the study information. If subject remains interested, a username and password to log into the study website will be emailed and the subject will be asked to read and electronically sign the informed consent within 1 week of the phone contact.
2. Following consent participants will be directed to complete the baseline questionnaire (APPENDIX G) electronically within 1 week of contact. This timeline is not required for study participation, if the subject completes the consent form and/or baseline questionnaires beyond the 1-week limit, they will still be enrolled in the study.
  - If the consent and baseline questionnaire are not completed within 1 week, SRC will call the participant to confirm their interest in enrolling and encourage participation.
  - Criteria in the baseline questionnaire must be negative prior to randomization.
3. When the consent is electronically signed and baseline questionnaire is completed and randomization will occur electronically through the website.

### 6.3 Intermediate Visits (8 weekly website visits during weeks 1 to 8)

Once enrolled in the study participants will be randomized to one of two arms.

1. *Traditional Self- Care*: control arm
2. *PACT*: Intervention arm

### **A. Traditional Self-Care Control Arm**

1. Participants randomized to the Traditional Self-Care arm will be electronically directed to the traditional self-care website landing page.
2. Traditional self-care material will be available for the participant to review via the website. This material is equivalent to what is typically given to patients in the dental clinic. Traditional self-care includes focusing on rest and healing through changes in chewing, diet, heat/cold, over the counter analgesics, and reducing strain from oral and sleeping habits.
3. Participant will also continue participate in usual care from their dentist such as a splint or anti-inflammatory medications as needed. Some patients may be under care of another healthcare provider, such as a physical therapist.
4. Adverse events will be recorded through the website assessments.

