## **6.4 Final Study Visits (Final Visits, Weeks 8 and 16)**

All participants will be asked to complete the final follow-up outcomes evaluation at 8 weeks from the beginning of the intervention and at 16-weeks (2 months after program end). This includes questions about any adverse events and outcomes as reported by the participants during or after the lessons.

Participants will receive weekly email reminders from the web-system to complete the post-intervention questionnaires. There is a 2-week window in the completion of questionnaires at the 8-week and 16-week post-intervention time periods. If the questionnaire has not been completed at the 2-week period, participants will receive up to 3 reminder calls from the study coordinator to identify the barrier to completing the questionnaires and facilitate its completion.

If after two more weeks of time have passed without completion, the questionnaire will be not evaluable, and therefore, considered missing data.

At the end of the 8 week outcome questionnaire, participants will complete several program evaluation questions. In addition, at least ten randomly-selected subjects will complete a semi-structured qualitative interview about their experience in the program.

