#### 8.1.3 *Serious Adverse Events*

A **serious adverse event (SAE)** is generally defined as any untoward medical occurrence that results in death, is life threatening, requires inpatient hospitalization or prolongation of existing hospitalization, results in persistent or significant disability/incapacity, or is a congenital anomaly.

The study intervention is a patient-centered self-management program for TMD pain. Potential participants with serious medical or psychiatric conditions are excluded from the study at initial screening. If study participants develop an increase in pain or other health concerns during the course of the study whether or not related to the study intervention would be considered an adverse event. The PACT program is a web-based, tailored 8-week program supported by a health coach to help enhance understanding, compliance, and success in self-management for TMD pain. There are self-report assessments at the end of each week throughout the entire program to monitor progress, compliance, adverse events, risk factors, and protective factors. If study subjects develop an aggravation of the pain or a new symptom that the subject attributes to the study intervention this would be considered an adverse event. This will be monitored by both self-report within the PACT program weekly assessments as well as by the dental professional who is caring for the patient. Adverse events will be reported to the Study Coordinator, the PI and the PO.

If participants screen for depression, we will provide a list of mental health providers who they can consult with to ensure their safety.

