## **8.4 Time Period and Frequency for Event Assessment and Follow-Up**

The investigator will report all study intervention-related SAEs and related unexpected AEs with start dates occurring any time after informed consent is obtained until 7 (for non-serious AEs) or 30 days (for SAEs) after the last day of study participation. At each study visit, the investigator will inquire about the occurrence of AE/SAEs since the last visit (or since the first procedure at the first active phase visit). The investigator will also review all source documentation related to study procedures for evidence of related AEs. Events will be followed for outcome information until they return to baseline or stabilize. Study intervention-related AEs will be followed until resolution or stabilization of the AE, after which the subject will be referred to a qualified clinician(s) for care and follow-up.

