### APPENDIX A: SCHEDULE OF EVENTS

Below is a schedule of events that include initial, intermediate, and final study visits, and all contacts with participants, e.g., telephone, website, screening, and other contacts includes the permissible time windows for study visits, For each visit, the purpose and description of what will occur at the visit.

Contacts with participant	Identification Phase	Telephone Screening Phase	Consent Phase	Intervention Phase	1 st Post-Intervention Phase	2 nd Post-intervention Phase	Interview Phase
Time Period (weeks)	Week 1 Pre-	Week 0 Pre-	Week 0 Pre-	Week 1-8 Intervention	Week 8 Post-	Week 16 Post-	Week 16 Post-
EMR List of TMD patients	X						
Demographics information	X	X					
Inclusion/ Exclusion Criteria		X					
Recruitment			X	X			
Consent/ HIPPA Form			X	X			
Baseline Questionnaire			X	X			
Intervention Compliance/ adherence				X			
Coach support				X			
Outcomes Compliance/ adherence					X	X	
8 week Questionnaire					X		
16 week Questionnaire						X	
Qualitative interviews							X
Adverse Event Reporting				X	X		

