#### II. Adverse Event Information

##### A. Definition

An **adverse event (AE)** is generally defined as any unfavorable and unintended diagnosis, symptom, sign (including an abnormal laboratory finding), syndrome or disease which either occurs during the study, having been absent at baseline, or if present at baseline, appears to

worsen. Adverse events are to be recorded regardless of their relationship to the study intervention.

A **serious adverse event (SAE)** is generally defined as any untoward medical occurrence that results in death, is life threatening, requires inpatient hospitalization or prolongation of existing hospitalization, results in persistent or significant disability/incapacity, or is a congenital anomaly.

If participants screen for depression and/or suicidal ideation, we will provide a list of mental health providers who they can consult with to ensure their safety.

The study intervention is a patient-centered self-management program for TMD pain. The PACT program is a web-based, tailored 8-week program supported by a health coach to help enhance understanding, compliance, and success in self-management for TMD pain. There are self-report assessments at the end of each week throughout the entire program to monitor progress, compliance, adverse events, risk factors, and protective factors. If study subjects develop an aggravation of the pain or a new symptom that the subject attributes to the study intervention this would be considered an adverse event. This will be monitored by both self-report within the PACT program weekly assessments as well as by the dental professional who is caring for the patient. In both cases, this will be reported to the PI and PO.

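### The adverse-event questions promised to all participants are missing from the printed week-8 and week-16 surveys, and a weekly adverse-event self-report is described only for PACT

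*Protocol*

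**What the plan says.** Section 6.3 of the Protocol uses the same sentence for the control arm and the PACT arm: "Adverse events will be recorded through the website assessments". Section 6.4 describes the week-8 and week-16 evaluations of all participants and adds: "This includes questions about any adverse events and outcomes as reported by the participants during or after the lessons".

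Section 8.4 states: "At each study visit, the investigator will inquire about the occurrence of AE/SAEs since the last visit". Its reporting window runs to 7 days (non-serious events) or 30 days (serious events) after the last day of participation. Section 8.5.1 has related events entered on a case report form at every visit. The opening of Section 8 gives participants the coordinator's telephone number, and Section 15.3 places safety data in a separate database.

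A weekly route is described in Section 8.1.3 and again in Appendix J, II.A, both times as part of the account of the PACT program: "There are self-report assessments at the end of each week throughout the entire program to monitor progress, compliance, adverse events". Worse pain, or a new symptom the participant attributes to the intervention, is to be "monitored by both self-report within the PACT program weekly assessments as well as by the dental professional" who cares for the patient. For controls, Section 5.7.2 says: "The control group will be able to download usual self-care pdfs from the website". No weekly assessment is described for them.

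In Appendix A the row "Adverse Event Reporting" is marked for the intervention phase and the first post-intervention phase. The week-16 column is blank.

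**The concern.** The text promises that adverse events will be asked about in both arms through the website and at both follow-ups, but the printed forms and the schedule do not deliver this. If the study is fielded as printed, events at weeks 8 and 16 would be recorded only if some unprinted form asks for them or the participant volunteers them.

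The shortfall does not fall equally on the arms. PACT participants are described as reporting every week, and nothing comparable is described for controls. More frequent asking finds more events, so the arms could show different counts with identical true risk.

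This matters even without a planned safety comparison. The annual report must say whether adverse-event rates agree with pre-study assumptions (Section 11.3). The study stops if the intervention is linked to adverse effects that put its safety in doubt (Section 5.6; Appendix J, III.D). Appendix J, III also allows a recommendation to stop one or more arms for safety. As the pilot tests methods for a multi-site trial, an uneven capture system would carry forward.

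**Working it through.** The documents give no figure on this point to reproduce. The check is a comparison of texts, a count and a short illustration.

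**1. Promise against printed form**

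| Place | Applies to | Adverse-event content |
|---|---|---|
| Section 6.3 A and B | both arms | website assessments record events |
| Section 6.4 | all participants, weeks 8 and 16 | questions are included |
| Appendix G, 8-week general survey (items 1 to 22) | as printed | none |
| Appendix G, 8-week PACT-only survey (items 1 to 28) | PACT | none |
| Appendix G, 16-week survey | as printed | none |
| Section 12, five main data instruments | study | no adverse-event form listed |
| Appendix A | not split by arm | marked to the week-8 phase, week 16 blank |

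The 8-week surveys skip from item 17 to item 19. This does not point to a dropped adverse-event item: on the 16-week survey, item 18 is the vigorous-activity question.

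**2. Scheduled self-report points per participant**

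Inputs: 8 weekly PACT assessments (Section 8.1.3; Appendix J, II.A) and 2 follow-ups (Section 6.4).

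- PACT: 8 + 2 = 10 if Section 6.4 is honoured; 8 + 0 = 8 with the surveys as printed.
- Control: 0 + 2 = 2 if Section 6.4 is honoured; 0 + 0 = 0 with the surveys as printed.

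Coach calls are not counted, because the call duties in Appendix D include no adverse-event inquiry.

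**3. The per-visit inquiry**

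Sections 8.4 and 8.5.1 apply to both arms. However, the visits in Sections 6.2 and 6.3 are website visits, and Section 7.1.1 makes every questionnaire self-administered except the qualitative interview. The reminder calls in Section 6.4 go only to late responders and concern barriers to completion. No scheduled staff contact to ask controls about adverse events after randomization is described, and the case report form is not reproduced.

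**4. Direction of a by-arm reading**

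Let p be a true risk common to both arms, and c the probability that an event is recorded. The expected count per arm of 40 (Section 11.2) is 40 × p × c. The spurious difference is p × (c in PACT − c in control). All values of p and c below are assumptions, with c in PACT set at 90%.

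| p | c in control | Expected PACT vs control | Spurious excess in PACT |
|---|---|---|---|
| 10% | 90% | 3.6 vs 3.6 | 0 points |
| 10% | 50% / 25% / 0% | 3.6 vs 2.0 / 1.0 / 0 | 4 / 6.5 / 9 points |
| 20% | 50% / 25% / 0% | 7.2 vs 4.0 / 2.0 / 0 | 8 / 13 / 18 points |
| 30% | 50% / 25% / 0% | 10.8 vs 6.0 / 3.0 / 0 | 12 / 19.5 / 27 points |

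The table only turns assumed capture rates into counts. It shows the direction whenever capture is higher in PACT. It does not estimate the size.

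**The case against.** A reader might infer that controls have no adverse-event instrument at all. The documents do not support that. Sections 8.4 and 8.5.1 set an inquiry and a case report form at each visit without limiting them to one arm, Section 6.3 schedules weekly website visits for both arms, and Section 15.3 keeps safety data in their own database. Absence from outcome surveys does not prove absence everywhere. The PACT weekly assessment is not reproduced either, so its adverse-event content also rests on description.

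A reader might also infer that a planned safety comparison is one-sided. None is planned. The final analysis in Protocol Section 11.4 and the SAP lists no adverse-event analysis, the Appendix J event tables have no arm column, and Appendix J, I.C keeps group-identifiable material out of adverse-event reports. The missing survey item and the blank week-16 cell affect both arms.

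Two more points are fair. Appendix G is visibly not the final item set: the printed baseline survey lacks the moderator scales and ends with program evaluation questions. And Section 8.1.3 counts increased pain as an adverse event, while both arms rate jaw pain and chewing limitation at weeks 8 and 16. Those items touch two of the five symptoms in Appendix J, Table 5 (jaw pain and difficulty chewing).

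All of this limits the claim, but three things remain. Section 6.4 promises questions that no printed follow-up survey contains. The jaw ratings do not ask about locking, clicking, fatigue, new symptoms or attribution. And a weekly adverse-event prompt is described for one arm only.

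**Conclusion.** The point holds as a should-fix matter. It is certain on the page that Sections 6.3 and 6.4 disagree with Appendix G as printed, and that Appendix A disagrees with Sections 6.4 and 8.4. It is probable, but not proven, that ascertainment is more intensive in PACT. That rests on the weekly assessments working as Section 8.1.3 and Appendix J describe, and on no equivalent unprinted weekly prompt existing for controls.

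A by-arm reading of event counts would then be biased against PACT. The documents contain neither event rates nor capture rates, so the size cannot be estimated. Reading expected counts per arm out of them would only return the assumptions put in. Nor do they support a claim that control-arm harms would go wholly unrecorded. What is weakened is the annual statement on event rates and any safety judgment about one arm.

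**What to change.** Add the same short adverse-event block to the week-8 and week-16 surveys of both arms, for example the five symptoms in Appendix J, Table 5 plus an item for any other new or worse problem. Extend the Appendix A adverse-event row to week 16. Reconcile Sections 6.3, 6.4, 8.1.3, 8.4 and 8.5.1 with Appendices A and G, stating what asks the question at a website visit and whether controls receive a weekly prompt.

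If event counts are ever shown by arm, base them on the common items and list events from the PACT-only weekly assessments separately.

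The cost is a few survey items, about one extra minute per survey, and a one-line schedule change. The change should precede data collection, because events that were never asked about cannot be reliably recovered later.
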